6.3. Secondary Efficacy Endpoints and Analysis

The secondary efficacy endpoints are listed in Section 1.1. Analysis will be based on mITT and PP analysis sets.

Missing data for the following secondary endpoints will be imputed using the MI method detailed in Section 6.2.2:

Statistical Analysis Plan

- the percentage of patients who experience a $\geq 30\%$ reduction in the weekly average of the daily average PI-NRS score at week 12
- the percentage of patients who experience a $\geq 50\%$ reduction in the weekly average of the daily average PI-NRS score at week 12
- change from baseline to week 12 in the weekly average of the daily worst PI-NRS score over the past 24 hours

There will be no imputation for missing data for all other secondary efficacy endpoints unless noted otherwise.

6.3.1. Change From Baseline to Week 12 in the Individual Components of the Fibromyalgia Impact Questionnaire Revised: Symptom Subscore, Impact Subscore, and Functional Subscore Score

The FIQR is a commonly used instrument in the evaluation of FM patients. It contains 21 questions in 3 domains: function (9 questions), overall impact (2 questions), and symptoms (10 questions). Questions are graded on a 0 to 10 numeric scale with 10 being the worst. All questions are framed in the context of the **last 7 days**. The sub-total scores (subscores) and total scores will be calculated by ICON using the scoring guidance [[The Revised Fibromyalgia Impact Questionnaire \(FIQR\): validation and psychometric properties](#)] and will be provided in the database. The sub-total score for each domain is the summation of scores in the domain. The function sub-total score ranges from 0 to 90; overall impact sub-total score ranges from 0 to 20; the symptoms sub-total score ranges from 0 to 100. According to the scoring guidance, the FIQR total score is calculated as (the function sub-total score divided by 3) + the overall impact sub-total score + (the symptoms sub-total score divided by 2). Thus FIQR total score ranges from 0 to 100.

The FIQR will be assessed at BAPS visit and visits 3 to 7 (weeks 1, 4, 8, 12, and 16).

The change from baseline in FIQR symptom sub-score, impact sub-score, functional sub-score, and total score will be analyzed, respectively, using a MMRM method with change from baseline in the FIQR score at weeks 4, 8, and 12 as the dependent variable, sex, age group at FM onset, week, treatment, and treatment by week interaction as fixed factors, and the baseline FIQR score as a covariate. ARH(1) for repeated observations within patients will be used, and the denominator degrees of freedom will be estimated using Kenward-Roger's approximation. Missing total score will be considered as missing at random.

Notes, if ARH(1) does not converge, then simpler covariance structures with less parameters will be used in the following order until the model converges: AR[1]; CSH; and CS.

The LS mean estimates for the mean change from baseline as well as the difference of the estimates between the fremanezumab and placebo group, with the corresponding SE, p-value and associated 95% CI will be provided. The results from all visits will be presented.

SAS codes are:

```
ODS OUTPUT LSMEANS= LS DIFFS = DIFF (WHERE = (AVISIT = _AVISIT));  
PROC MIXED DATA= name;
```

```
CLASS SUBJID TRT01PN AVISIT AGEATFMONSET SEX;
```

Statistical Analysis Plan

```
MODEL CHANGE= BASE TRT01PN AGEATFMONSET SEX AVISIT  
TRT01PN*AVISIT/DDFM=KR;  
REPEATED AVISIT/SUBJECT= SUBJID TYPE= ARH(1);  
LSMEANS TRT01PN*AVISIT / DIFF CL;  
RUN;  
ODS OUTPUT CLOSE;
```

Where AVISIT denotes the study visit/week; BASE denotes the baseline value for the FIQR scores.

In addition, the FIOR scores will be summarized using descriptive statistics for all visits.

6.3.2. The Patient Global Impression of Change Rating at Week 12

The PGIC scale evaluates all aspects of patients' health and assesses if there has been an improvement or decline in clinical status since the start of the study. Patients will record responses to the PGIC scale visits 6 and 7 (weeks 12 and 16). Improvement is recorded on a 7-point scale, with 1 indicating very much improved, 4 indicating no change, and 7 indicating very much worse:

- 1 = Very Much Improved
- 2 = Much Improved
- 3 = Minimally Improved
- 4 = No Change
- 5 = Minimally Worse
- 6 = Much Worse
- 7 = Very Much Worse

For analysis purpose, a dichotomous scale of 'Yes' or 'No' will be derived. Scale "much improved" or "very much improved" will be considered improved (Yes), and all other non-missing responses will be considered not improved (No). Missing category will be presented as appropriate.

The response variable (yes or no) at week 12 will be analyzed using a logistic regression model with the treatment, age group at FM onset, and sex as explanatory factors. Missing category will not be included.

SAS code is:

```
ods output diffs = dif LSMeans = ls;  
PROC GENMOD DATA =name;  
CLASS TRT01PN STRATAR SEX;  
MODEL AVALCAT1 = TRT01PN STRATAR SEX / DIST=BIN TYPE3;  
LSMEANS trt01pn/exp DIFF CL;  
RUN;  
ods output close;
```

Statistical Analysis Plan

```
data ls;
set ls;
** p = estimated response rate;
p = logistic(estimate);
p_l = logistic(Lower);
p_u = logistic(Upper);
run;
```

Where AVALCAT1 denotes the responses with ‘yes’ for improved and ‘no’ for not improved.

In addition, the PGIC data will be summarized as a categorical variable using descriptive statistics for all visits, including missing category as appropriate.

6.3.3. Percentage of Patients Who Experience a $\geq 30\%$ or $\geq 50\%$ Reduction in the Weekly Average of the Daily Average PI-NRS Score at Week 12

The weekly average of the daily average PI-NRS score with missing data imputation from the 500 imputed data sets derived as described in steps 1 to 3 of Section 6.2.2 will be used to calculate the pain intensity reduction (%) from baseline in the weekly average of the daily average PI-NRS score using formula [2].

$$\frac{\text{baseline value} - \text{postbaseline value}}{\text{baseline value}} \times 100\% \quad [2]$$

The percentage of patients who experience $\geq 30\%$ reduction and $\geq 50\%$ reduction in the weekly average of the daily average PI-NRS score at week 12 will be analyzed using a generalized estimating equation (GEE) method where the dependent variable is $\geq 30\%$ reduction (Yes/No) or $\geq 50\%$ reduction (Yes/No), respectively, [REDACTED]

SAS code for GEE model:

```
ods output LSMeans = ls;
PROC GENMOD DATA =name;
  BY _IMPUTATION_;
  CLASS SUBJID TRT01PN WEEK STRATAR SEX;
  MODEL AVALCAT = BASE TRT01PN WEEK STRATAR SEX
          TRT01PN*WEEK/ DIST=BIN TYPE3;
  REPEATED SUBJECT = SUBJID / TYPE = AR(1);
  LSMEANS trt01pn*week/exp DIFF CL;
RUN;
ods output close;
```

Where AVALCAT denotes the responses with ‘yes’ for $\geq 30\%$ or $\geq 50\%$ or ‘no’ for $< 30\%$ or $< 50\%$ pain intensity reduction, respectively.

The 500 sets of results from above analyses will be combined using Rubin’s formulae (PROC MIANALYZE).

```
PROC SORT DATA= LS;
```

Statistical Analysis Plan

```

    BY WEEK TRT01PN _IMPUTATION_ ;
RUN;

ODS OUTPUT PARAMETERESTIMATES= LSM_O;
PROC MIANALYZE DATA= LS;
    BY WEEK TRT01PN;
    MODELEFFECTS ESTIMATE;
    STDERR STDERR;
RUN;

DATA LSM_O;
    SET LSM_O;
    EXPESTIMATE = EXP(ESTIMATE);
    P = 100*EXPESTIMATE/(1 + EXPESTIMATE);
    P_LL = 100*EXP(LCLMEAN)/(1 + EXP(LCLMEAN));
    P_UL = 100*EXP(UCLMEAN)/(1 + EXP(UCLMEAN));
RUN;

```

In addition, the mean percentage of reduction and its associated 95% CI will be reported by week.

A plot of percentage of improvement versus percentage of patients meeting the improvement level at week 12 will be presented based on observed data and missing data at week 12 will be deemed as pain intensity increased from baseline. The x-axis representing percentage of improvement will be from ≥ 0 to 100% by an increment of 10%, ie., the x-axis will be at cutoff points $\geq 0\%$, $\geq 10\%$, $\geq 20\%$, ..., $\geq 90\%$ and 100% while y-axis will be percent of patients meet the cutoff points. The percentage of improvement will be calculated using formula [2].

6.3.4. Change From Baseline to Week 12 in the Weekly Average of the Daily Worst PI-NRS Score Over the Past 24 Hours

The weekly average of the daily worst PI-NRS score over the past 24 hours will be analyzed in a manner analogous to the primary endpoint as described in Section 6.2.2. The dependent variable is the change from baseline in the weekly average of the daily worst PI-NRS scores. The covariate will be baseline average of the daily worst PI-NRS scores.

6.3.5. Change From Baseline to Week 12 in the Patient-Reported Outcomes Measurement Information System Sleep Disturbance Short Form 8a Score

The PROMIS sleep disturbance Short Form 8a (SF8a) scale contains 8 items and assesses sleep disturbance over the past 7 days. One item assessing overall sleep quality use a scale of *very poor, poor, fair, good, or very good*. Other 7 items use a scale of *not at all, a little bit, somewhat, quite a bit, or very much*. Each item of the PROMIS sleep disturbance SF8a is on 5-point scales (1 to 5), with 1 for the lowest sleep disturbance and 5 for the highest sleep disturbance. The total score ranges from 8 to 40 (highest sleep disturbance). Collection of the PROMIS sleep disturbance SF8a will start the day of the BAPS Visit (Visit 2) and will be administered weekly via the e-diary. The total raw score ranging from 8 to 40 (highest sleep disturbance) will be calculated as the summation of 8 non-missing scores. If any of 8 items has a missing score, the total raw score will be missing. The calculated total raw score will be converted into t-score

using the scoring table ([PROMIS-Sleep Disturbance Scoring Manual](#)). All questions must be answered in order to produce a valid score using the scoring table. The analysis will be based on t-score.

The change from baseline to week 12 in t-score of the PROMIS sleep disturbance SF8a will be analyzed using MMRM method in manner analogous to the analysis as described in Section 6.3.1. The dependent variable is the change from baseline in the t-score of the PROMIS sleep disturbance SF8a at analysis weeks 1 to 12 (12 levels). BASE is the t-score of the PROMIS sleep disturbance SF8a at baseline. Missing will be considered as missing at random. The results from all visits will be presented using descriptive statistics.

Summary statistics will include data from all analysis weeks.

6.3.6. Change from Baseline to Week 12 in the Patient-Reported Outcomes Measurement Information System Physical Function SF12a Score

The PROMIS physical function scale measures self-reported capability rather than actual performance of physical activities. This includes the functioning of one's upper extremities (dexterity), lower extremities (walking or mobility), and central regions (neck, back), as well as instrumental activities of daily living, such as running errands over the past 7 days. A single physical function capability score is obtained from a SF. The PROMIS physical function SF12a scale contains 12 items with 5-point scales (1 to 5) for each item with a total score ranging from 12 to 60. A lower score indicates more limited physical disability.

The PROMIS physical function SF12a will be assessed at BAPS Visit (visit 2) and visits 3 to 7 (weeks 1, 4, 8, 12, and 16).

The total raw score will be calculated as the summation of 12 non-missing scores for patients who can walk 25 feet or summation of 6 non-missing scores for patients who cannot walk for 25 feet. The calculated total raw score will be converted into scale score using the scoring tables ([PROMIS-Physical Function Scoring Manual](#)). Different scoring tables will be used for patients who can walk and patients who cannot walk. All questions must be answered in order to produce a valid score using the scoring table. The analysis will be based on the scale score.

The change from baseline to week 12 in the scale score of PROMIS physical function SF12a will be analyzed using MMRM method in manner analogous to the analysis as described in Section 6.3.1. The dependent variable is the change from baseline in the scale score of PROMIS physical function SF12a at weeks 4, 8, and 12 (3 levels). BASE is the scale score of PROMIS physical function SF12a at baseline. Missing will be considered as missing at random. The results from all visits will be presented using descriptive statistics.

Summary statistics will include data from all visits.

6.3.7. Change From Baseline To Week 12 In The Patient-Reported Outcomes Measurement Information Fatigue SF8a Score

The PROMIS Fatigue SF8a contains 8 items with 5-point scales (1 to 5) for each item over the past 7 days. The total score ranges from 8 to 40 (highest level of fatigue). The PROMIS fatigue SF8a will be assessed at BAPS Visit (visit 2) and visits 3 to 7 (weeks 1, 4, 8, 12, and 16).

Statistical Analysis Plan

The total raw score will be calculated as the summation of 8 non-missing scores. The calculated total raw score will be converted into t-score using the scoring table ([PROMIS-Fatigue Scoring Manual](#)). All questions must be answered in order to produce a valid t-score using the scoring table. The analysis will be based on t-score.

The change from baseline to week 12 in the t-score of the PROMIS Fatigue SF8a will be analyzed using MMRM method in manner analogous to the analysis as described in Section 6.3.1. The dependent variable is the change from baseline in the t-score of the PROMIS Fatigue SF8a at weeks 4, 8, and 12 (3 levels). BASE will be the t-score of PROMIS fatigue SF8a from the baseline. Missing will be considered as missing at random. The results from all visits will be presented using descriptive statistics.

Summary statistics will include data from all visits.

6.3.8. Number (%) of Patients Who Did Not Complete the Treatment Due to Lack of Efficacy

Time to treatment discontinuation will be assessed for all patients and will be measured from the date of the first dose of study medication to the date of treatment completion or treatment discontinuation before visit 7. Time to treatment discontinuation is defined as the date of EOT - the date of 1st dosing of IMP + 1. Patients who completed the treatment will be censored at the date of EOT. Patients who did not complete the treatment due to reasons other than lack of efficacy will be censored at the date of ET. Patients who are lost to follow-up will be censored at the date of their last visit.

Time to treatment discontinuation will be analyzed using Kaplan-Meier survival analysis method. Number (%) of patients who do not complete the treatment due to lack of efficacy (the event) and patients censored will be presented. Kaplan-Meier estimates (median time to treatment discontinuation due to lack of efficacy, survival probability at weeks 4, 8, 12 and 16) and survival plot will also be presented.

6.4. [Redacted]

[Redacted]

6.4.1. [Redacted]

[Redacted]

[Redacted]

[Redacted]

• [REDACTED]

[REDACTED]

[REDACTED]

[REDACTED]

[REDACTED]

6.4.2. [REDACTED]

[REDACTED]

[REDACTED]

[REDACTED]

[REDACTED]

6.4.3. [REDACTED]

[REDACTED]

[REDACTED]

[REDACTED]

[Redacted text block]

6.4.4. [Redacted text block]

6.4.5. [Redacted text block]

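### The GENMOD code for the PGIC and pain-responder endpoints names no event level, so with the SAP's own yes/no coding it outputs non-response rates

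*SAP*

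**What the plan says.** SAP 1.1 and 6.1 define the PGIC endpoint as the share of patients much or very much improved at week 12. The pain endpoints are the shares with at least a 30% or 50% reduction.

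For PGIC, SAP 6.3.2 dichotomises the scale, leaves missing responses out of the model, and explains the coding: "Where AVALCAT1 denotes the responses with ‘yes’ for improved and ‘no’ for not improved". The procedure call is "PROC GENMOD DATA =name", followed by "MODEL AVALCAT1 = TRT01PN STRATAR SEX / DIST=BIN TYPE3". A data step then applies the inverse logit, "p = logistic(estimate", under a comment that reads "p = estimated response rate". The block saves both LS means and treatment differences.

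For the pain responders, SAP 6.3.3 uses the same kind of coding ("Where AVALCAT denotes the responses with ‘yes’ for" patients at or above the cut) and a GEE whose model line begins "MODEL AVALCAT = BASE TRT01PN WEEK STRATAR SEX" and also ends in a binomial distribution with no level option. Only LS means are saved. They are pooled over the 500 imputations and converted to a percentage by "P = 100*EXPESTIMATE/(1 + EXPESTIMATE", closing bracket following.

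Neither block contains `EVENT=`, `REF=`, `DESCENDING` or `ORDER=`, and neither conversion takes a complement. SAP section 17 fixes the software as SAS 9.4 or later.

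**The concern.** A binary model in SAS needs to know which of the two levels is the event. If nobody says, the software chooses by sort order, and no sorts before yes. The fitted quantity is then the probability of not responding, while the PGIC comment calls it the response rate and SAP 6.3.3 presents it as the percentage for an endpoint defined by success.

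Three secondary efficacy endpoints share this code. SAP 1.1 states the primary objective as estimation of a treatment effect, and SAP section 7 plans no multiplicity adjustment. In such a study the secondary results will be read from rates, intervals and direction, which are the quantities at risk here. An active arm with more responders would be tabulated with the lower rate.

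**Working it through.** The plan gives no response rate or odds ratio for these endpoints, so there is no stated figure to reproduce. The check is on the code.

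**Inputs.** From SAP 6.3.2 and 6.3.3: yes/no coding, no event option, and an inverse-logit back-transformation without a complement. From outside the documents: GENMOD's default of modelling the first ordered level. The documents do not state this default, so it is an assumption of the check.

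**Step 1, sort order.** The levels sort as no < yes. No/Yes, N/Y and 0/1 give the same order. The modelled event is therefore non-response under any of these codings.

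**Step 2, what the back-transformation returns.** Let η be the LS mean on the logit scale when yes is the event. Because logit P(no) = −logit P(yes), modelling no changes the sign of every coefficient and of every LS mean. The printed value is

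exp(−η) / (1 + exp(−η)) = 1 − exp(η) / (1 + exp(η)),

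which is one minus the response rate. The confidence limits become one minus the correct limits, in reversed order. Covariates do not alter this. Nor does Rubin pooling, since the mean of the −η values is minus the mean of the η values.

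**Step 3, the odds ratio (PGIC only).** The difference in LS means also changes sign, so the exponentiated difference is 1/OR.

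**Step 4, size under assumed rates.** The documents give no rates, so these are illustrations across a range.

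| Assumed response, placebo/active | Printed, placebo/active | Correct OR | Printed OR (PGIC) |
|---|---|---|---|
| 20% / 30% | 80% / 70% | 1.714 | 0.583 |
| 25% / 35% | 75% / 65% | 1.62 | 0.62 |
| 30% / 40% | 70% / 60% | 1.556 | 0.643 |
| 30% / 50% | 70% / 50% | 2.333 | 0.429 |

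For the second row: OR = (0.35/0.65) / (0.25/0.75) = 1.62, and 1/1.62 = 0.62.

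**Step 5, fitting both ways.** A binomial-logit model with 80 patients per arm, without the sex and age-group terms, was fitted with each level as the event. For 30%/40%:

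- Event yes: 30% (95% CI 21.0 to 40.9) and 40% (29.9 to 51.0), OR 1.556, p = 0.186.
- Event no: 70% (59.1 to 79.0) and 60% (49.0 to 70.1), OR 0.643, p = 0.186.

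The two-sided p-values were also identical for 20%/30% (0.146) and 30%/50% (0.0105).

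**The case against.** The strongest reply is that the endpoint definitions in the text are correct and only template code is incomplete. The input dataset is a placeholder name, and the SAP says what the responses denote, not how the variables are stored or formatted. A coding or format that puts the responder level first would give the intended rates. This stands as a condition on the conclusion. It does not rescue the code, because the coding that the SAP itself gives leads to the wrong level.

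A second reply is that other outputs would expose the error. PGIC is also tabulated by category at all visits and in subgroups (SAP 6.2.4 and 6.3.2), and SAP 6.3.3 plots the observed share of patients reaching each improvement level at week 12. These might prompt a correction but do not make one. The plot is also a weak check on the pain rates: it counts missing values as worsening, so it will differ somewhat from the imputed GEE rates in any case.

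Third, part of the model description in SAP 6.3.3 is redacted, so it cannot be excluded that the hidden text names the event. The printed code that follows does not.

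A reader might infer that all three endpoints would carry an inverted odds ratio. The documents do not support that. The 6.3.3 code saves and pools LS means only, so no treatment odds ratio is carried forward for the 30% and 50% endpoints. Even for PGIC, the SAP saves the differences without saying that an odds ratio will be reported.

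**Conclusion.** The code in SAP 6.3.2 and 6.3.3 is wrong as written, with moderate severity. If the stored values follow the SAP's yes/no coding and GENMOD's default applies, the PGIC and pain-responder percentages come out as one minus the intended rate, with complementary limits, and any real difference between arms is reversed in direction. The size depends on the true rate: 25% would print as 75% and 40% as 60%, while a rate of 50% would look unchanged. For PGIC the saved treatment contrast is inverted as well.

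A reader might go further and take this as a threat to the study's main conclusions. The documents do not support that. Two-sided p-values are the same whichever level is modelled, the primary MMRM does not use this code, and the SAP records that the study had already been stopped for futility under separate interim plans. The problem is confined to the estimates and direction reported for three secondary endpoints.

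**What to change.** Name the event on the response in both MODEL statements: `AVALCAT1(EVENT='yes')` in SAP 6.3.2 and `AVALCAT(EVENT='yes')` in SAP 6.3.3. The quoted value must match the stored or formatted value exactly, and the SAP writes both Yes and yes, so the case needs to be settled first. The alternative is `DESCENDING` on both PROC GENMOD statements. That still relies on sort order and would itself pick the wrong level if the responder level sorts first, so naming the event is safer.

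Add one verification step: confirm the modelled level in the SAS log and compare the model-based rates with the raw percentages by arm. The cost is one option in each of two code blocks plus that check, and the intended analysis does not change.

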2. STUDY DESIGN

2.1. General Design

This is a 21-week, multicenter, randomized, double-blind, placebo-controlled, parallel-group study to evaluate the efficacy and safety of fremanezumab in adult patients with FM. Fremanezumab 225 mg, fremanezumab 675 mg, or placebo will be administered sc for 4 monthly doses. The study will consist of a 17- to 35-day screening period (Visit 1, phone contact, a Baseline Assessment Period Start [BAPS] Visit [Visit 2]), and a 16-week double-blind treatment period (Visits 3, 4, 5, 6, and 7). Patients enrolled in the study will be male or female patients with FM with an average of the daily average PI-NRS score of ≥ 4 and ≤ 9 during the 14-day baseline assessment period. Patients will be required to wash out of all prohibited concomitant medication(s) prior to the BAPS Visit (Visit 2).

[figure not shown]
Therefore, the total duration of patient participation in the study is planned to be 21 weeks, consisting of the screening period of up to 5 weeks (ranging from 17 to 35 days) and the double-blind treatment period of 16 weeks. The end-of-study (EOS) is defined as completion of the last visit of the last patient.

Note, there was the 14-week follow-up period prior to Study TV48125-PN-20028 protocol amendment 04.

The study schematic diagram is presented in [Figure 1](#).

Study procedures and assessments with their timing are summarized in Table 1 of the study protocol.

Figure 1: Overall Study Schematic Diagram

^a The screening period is up to 5 weeks and can range from 17 to 35 days. The duration of the washout period will be 7 to 19 days; suggested washout periods for commonly used analgesics are listed in the study protocol. Note: For Visits 4 and 5 (when at-home dosing is available), home visits are permitted for patients who are not able to go to the investigational center or if the investigational center staff are not able to see patients at the investigational center.

BAPS = Baseline Assessment Period Start; COVID-19 = Coronavirus Disease 2019; e-diary = electronic diary; EOS = end-of-study; EOT = end-of-treatment; PK = pharmacokinetic; sc = subcutaneous; V = visit.

The follow-up period (14 weeks) in the protocol was removed in Study TV48125-PN-20028 protocol amendment 04. The data collected in the follow-up period will be listed.

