2.4. Sample Size and Power Considerations

The sample size of 80 subjects per treatment group was selected based on expert consensus agreement at a scientific advisory board meeting; this sample size is expected to provide sufficient precision to estimate the treatment effect of fremanezumab versus placebo. Moreover, assuming a standard deviation (SD) of 2.2 for change from baseline in the weekly average of the daily average PI-NRS score, 80 patients per treatment group will provide at least 90% probability to observe the half length of the 95% confidence interval (CI) of the treatment difference between fremanezumab 225 mg sc or fremanezumab 675 mg sc and placebo less than 0.74. In total, 240 patients will be enrolled in this study in a 1:1:1 randomization ratio.

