PROC MI DATA= MI_MONOTONE NIMPUTE= 1 SEED= 4751523
OUT= MI_COMPLETE;
  CLASS TRT01PN AGEATFMONSET SEX;
  MONOTONE REG;
  VAR TRT01PN AGEATFMONSET SEX BASE WEEK1 ... WEEK12;
RUN;
```

MI_COMPLETE will be transposed to a new data set (WEEKPI0) with each week as a row.

Step 3: Use by-week mean change from baseline to adjust those who discontinued treatment due to lack of efficacy (LOE) or adverse event (AE) before week 12.

The initially missing and now imputed data for patients who discontinued from the study drug due to LOE or AE will be center adjusted at the mean baseline value. That is, the final imputed score will be equal to the imputed score under missing at random minus the observed mean change from baseline score at the post baseline time point.

```
DATA WEEKPI;
  SET WEEKPI0;
  CHANGEi = AVALi - BASE;
  IF DTREAS IN ('LACK OF EFFICACY', 'ADVERSE EVENT') AND IMP= 1
  THEN DO;
    CHANGEi = CHANGEi - MWEEK_CHG;
  END;
RUN;
```

Where AVALi denotes the value of the post baseline weekly average of the daily average PI-NRS after missing data imputation; CHANGEi denotes the change from baseline after missing data imputation; MWEEK_CHG denotes the change from baseline calculated without missing data imputation; DTREAS denotes the reason for treatment discontinuation.

Step 4: Each of the 500 imputed data sets described above steps will be analyzed using the MMRM. SAS code is:

```
ODS OUTPUT LSMEANS= LS DIFFS = DIFF (WHERE = (week = _week));
PROC MIXED DATA= WEEKPI (WHERE= (WEEK>= 1));
  BY _IMPUTATION_;
  CLASS SUBJID TRT01PN WEEK AGEATFMONSET SEX;
  MODEL CHANGEi= BASE TRT01PN AGEATFMONSET SEX WEEK
    TRT01PN*WEEK/DDFM=KR;
  REPEATED WEEK/SUBJECT= SUBJID TYPE= ARH(1);
  LSMEANS TRT01PN*WEEK / DIFF CL;
RUN;
ODS OUTPUT CLOSE;
```

Statistical Analysis Plan

Where `_IMPUTATION_` denotes the numbering of imputations; `SUBJID` denotes the subject ID; `WEEK` denotes the analysis week (12 levels: weeks 1 to 12).

Step 5: The results from the 500 analyses from Step 4 will be combined using Rubin’s formulae (`PROC MIANALYZE`). The least square (LS) mean estimates for the mean change from baseline to each time point, as well as the difference of the estimates between the fremanezumab and placebo group, with the corresponding SE, p-value and associated 95% CI will be provided.

(a) For LS means

```
PROC SORT DATA= LS;  
  BY WEEK TRT01PN _IMPUTATION_ ;  
RUN;  
  
ODS OUTPUT PARAMETERESTIMATES= LSM_O;  
PROC MIANALYZE DATA= LS;  
  BY WEEK TRT01PN;  

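### SAP 6.3.3 has no non-responder rule for patients who stop for lack of efficacy or an adverse event, and the Step 3 adjustment may not reach the 30%/50% responder variable

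*SAP*

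**What the plan says.** SAP 6.3 sends the 30% and 50% responder endpoints through the multiple imputation of SAP 6.2.2. SAP 6.3.3 states that the 500 "imputed data sets derived as described in steps 1 to 3 of Section 6.2.2 will be used to calculate the pain intensity reduction". Formula [2] divides baseline minus post-baseline value by baseline, and the result is coded yes or no for a GEE model.

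In SAP 6.2.2, Steps 1 and 2 impute under missing at random, given baseline and all preceding weeks. Step 3 applies to imputed values of patients who stopped for LOE or an AE. Its text says that the imputed score is reduced by the observed mean change, so that these patients are back at baseline on average. Its code does this through "CHANGEi = CHANGEi - MWEEK_CHG". `AVALi`, defined there as the weekly score after imputation, is not changed.

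SAP 1.4 says that no efficacy data are collected after discontinuation before week 12. For the plot of response against cutoff, SAP 6.3.3 uses observed data, and "missing data at week 12 will be deemed as pain intensity increased from baseline".

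Neither SAP 6.3.3 nor Protocol 9.6.4.3 visibly sets LOE or AE stoppers to non-response. Part of the GEE sentence in SAP 6.3.3 is blacked out. The matching protocol sentence gives the link and the model factors at that place, not a missing-data rule.

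**The concern.** A responder should be a patient who obtained meaningful relief on treatment. A shift to baseline on average suits an analysis of means. Once the values are dichotomised, the favourable tail of the spread becomes responders although nobody was observed to respond. The arm that loses more patients this way, particularly to adverse events, gains more such responders. If the programmer takes `AVALi` as the post-baseline value, the shift is lost as well, and the responder analysis departs from the assumption behind the primary endpoint. The section would also show two response levels at one week under different rules, without telling the reader why.

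**Working it through.** **1. The plan's own figure.** SAP 2.4 gives no design figure for the responder endpoints. It gives one for the primary endpoint, "assuming a standard deviation (SD) of 2.2 for change from baseline in the weekly average of the daily average PI-NRS score". At that SD and with 80 per arm, it puts the chance that a pairwise 95% interval has a half-length under 0.74 at 90% or more. The half-length is t(0.975, 158) × s × √(2/80), with 158 s²/2.2² distributed as chi-square on 158 df. The probability that it is below 0.74 is 0.918 at 80 per arm and 0.897 at 79. The figure reproduces, so SD 2.2 is used below.

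**2. Drop needed.** SAP 2.1 puts the baseline average between 4 and 9. A 30% response needs 0.3 × 4 = 1.2 to 0.3 × 9 = 2.7 points. A 50% response needs 2.0 to 4.5.

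**3. What the shift leaves.** Step 3 subtracts a constant, so the spread is unchanged. If the shifted change is normal around 0 with SD 2.2, P(response) = Φ(−f × B / 2.2) for cutoff f and baseline B:

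| Baseline | 30% cutoff | 50% cutoff |
|---|---|---|
| 4 | Φ(−0.545) = 29% | Φ(−0.909) = 18% |
| 6 | Φ(−0.818) = 21% | Φ(−1.364) = 9% |
| 9 | Φ(−1.227) = 11% | Φ(−2.045) = 2% |

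These draws ignore the patient's earlier weeks. They show only that the tail is not empty.

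**4. Text against code.** Formula [2] equals −(post-baseline − baseline)/baseline. With the adjusted `CHANGEi` it is −`CHANGEi`/`BASE`, and the shift is kept. With `AVALi` the shift is lost. Take baseline 6, observed mean change −1.5 and an imputed change of −2. With `AVALi` the reduction is 2/6 = 33%, a 30% responder. With the shift the change is −2 + 1.5 = −0.5, a reduction of 8%, a non-responder.

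**5. Simulation conditional on earlier weeks.** This followed the monotone regression imputation, with treatment, baseline and preceding weeks as predictors (sex and age at onset omitted), and then Step 3. Assumptions, none given in the documents:
- baseline mean 6.5, SD 1.2, kept within 4 to 9
- SD rising from 1.3 to 2.2 over 12 weeks
- AR(1) correlation 0.8, 0.9 or 0.95
- mean change approaching −1, −1.5 or −2
- 15% stopping, half for LOE (drawn from those improving least) and half for an AE (drawn at random)
- 80 per arm, 60 trials, 5 imputations each

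| Counted as responders | AE stoppers | LOE stoppers |
|---|---|---|
| 30%, shift applied | 17-20% | 0.5-7.5% |
| 50%, shift applied | 6-8% | 0.1-2.5% |
| 30%, shift lost | 35-53% | 3-30% |
| 50%, shift lost | 17-30% | 1-14% |
| Plot rule, either cutoff | 0% | 0% |

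**6. Effect on an arm's 30% rate.** No stopping rate is given. Assume 10%, that is 8 of 80. With the shift, the lowest case is all LOE, 10% × 0.5% = 0.05 points, and the highest is all AE, 10% × 20% = 2 points. Without the shift, the range is 10% × 3% = 0.3 to 10% × 53% ≈ 5 points.

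**The case against.** The Step 3 text adjusts the score itself, formula [2] can be written as −`CHANGEi`/`BASE`, no code deriving the responder variable is printed, and citing Step 3 would be pointless if its adjustment were dropped. Scatter around baseline is ordinary multiple imputation, and using the same data sets keeps this endpoint aligned with the primary analysis. The plot declares itself based on observed data and treats all missing values alike. The table reports model-adjusted GEE estimates, which need not equal raw proportions under any rule. These are secondary endpoints without multiplicity control, in a proof-of-concept study already stopped for futility.

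Much of this stands. A reader might infer that the plan definitely feeds unadjusted scores into the responder endpoint. The documents do not support that: the code leaves room for it and the text points the other way. A reader might also take a marginal draw at baseline 6.5, Φ((−1.95 + 1.5)/2.2) = 42%, as the share of stoppers counted as responders, and so about 4 points per arm at 10% stopping. That is not the plan's imputation, which conditions on preceding weeks and gives LOE stoppers much lower chances. Nor must table and plot agree.

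Two things survive. Alignment with the primary analysis does not make a dichotomised tail meaningful for treatment failures. And text and code disagree on the variable that this endpoint may use.

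**Conclusion.** The point holds in a limited form. On the visible text, patients who stop for LOE or an AE can be counted as 30% or 50% responders. With the Step 3 shift the effect is modest and comes mainly from AE stoppers, adding at most about 2 points to an arm's 30% rate when 10% stop. If the shift is lost through `AVALi`, it can reach about 5 points. These sizes rest on the assumed correlation, mean change, baseline distribution and stopping rate.

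The plot's opposite rule covers missing data for any reason, so table and plot differ for other dropouts too. That calls for a clear label and does not make either display wrong. A patient who stops during week 12 with at least one diary entry is observed in both analyses. The primary MMRM uses the adjusted `CHANGEi` and is not affected. The change is worth making, but the plan's main conclusion does not depend on it.

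**What to change.** In SAP 6.3.3, set responder = No in every imputed data set for weeks after treatment discontinuation for LOE or an AE whose score is imputed. Leave observed weeks untouched, and keep the imputed scores for other missing data. At minimum, set `AVALi = BASE + CHANGEi` after Step 3, so that formula [2] uses the adjusted score. Label the plot as observed data with all missing values counted as failure; it need not be rebuilt over the imputations.

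The cost is a sentence or two in SAP 6.3.3, a line of code and a figure note. Response rates become slightly lower, and LOE and AE stoppers are handled more strictly than under the primary analysis's on-average return to baseline, which the SAP should state. SAP 2.5.2 places SAP amendments before database lock, with treatment codes still blinded, so the rule can be prespecified.
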